Expanding the Click City Tobacco Prevention Program
to Include E-cigarettes and Other Novel Tobacco Products

Study Protocol and Statistical Analysis Plan

NCT 036872900
March 6, 2023

Study Protocol and Statistical Analysis Plan

Design of the Effectiveness Trial

We recruited 44 schools across Oregon (N=18) and Arizona (N=26), stratified them by state and size of the school (small, medium, large), yoked them according to their desired start dates, and randomized them to intervention (received the *Click City®: Tobacco* program) or control (implemented their standard curriculum). Schools were randomized after they agreed to participate in the trial and signed a Memorandum of Understanding. For students in the intervention schools, participation in the trial consisted of a baseline assessment one-week prior to starting the program, completing two lessons a week over a four-week period, and a follow-up assessment one-week following completion of the program. To control for the effect of history, students in control schools completed the baseline and follow-up assessments during the same week as students in their yoked intervention school.

We began the effectiveness trial in January of 2020, and by March 13, a total of 26 schools had completed their participation in the trial (16 schools in Arizona and 10 schools in Oregon). At that time, schools in both Arizona and Oregon were ordered to close due to the COVID-19 Pandemic. After schools re-opened, we were able to recruit an additional 17 schools and used the same procedure as that used prior to the pandemic to randomize them. Among the 44 anticipated schools, 43 completed the trial, and 22 schools were assigned to the intervention arm and 21 schools to control.

Procedures

A school liaison was selected within each school to facilitate the trial. A research assistant (RA) contacted the liaison and provided an overview of how the program worked and offered troubleshooting assistance should any issues arise with the program. The RA entered the school, district and the participating 5th grade teacher's name(s) and email(s) within the

administrative portal. The liaison sent a link and instructions to teachers the week before they were to begin the program. This process is like what we expect in a “real-world” setting when the program is marketed.

Each teacher set-up their respective account by entering their basic information and naming their class. The program automatically generated a unique class code to share with their students. When the student first logged into the program, they entered their class code, their name, birthdate, student ID, and a unique username. This information populated the class roster in the teacher’s portal. Teachers had the ability to view and edit each student’s name, username, birth date and student ID. They also had the ability to track each student’s progress through the program. If necessary, they could change the standard administration of the program of one lesson a day and two lessons a week over four weeks, allowing individual students or their entire class to do two or more lessons a day.

Assessments. Upon prompting by the research assistant, teachers facilitated the baseline assessment, one week prior to program implementation, and the follow-up assessment, one-week following the last activity in the program. Assessments were completed using Qualtrics in the school setting. The measures assessing the outcomes and etiological mechanisms associated with e-cigarette use were like measures assessing outcomes and mechanisms associated with cigarette use used in the previous efficacy trial of the original version of *Click City®: Tobacco* (Andrews, et al., 2011).

Analysis Strategy

The sample consisted of those who completed the baseline and/or the follow-up assessment in 5th grade. This approach maximized the 5th grade sample and missing data was estimated using full information maximum likelihood methods. This intent to treat approach assumed that all those who completed at least one assessment participated in Click City: Tobacco and received the entire intervention or their usual curriculum.

Data were analyzed using a general linear mixed model with students nested within schools and schools nested within condition using the GLM procedure within SPSS, version 24. Since schools were randomized to condition, both the student and the school were random effects. Using this method, we examined the effect of the intervention on changes in major outcomes and all etiological mechanisms that were targeted in the program.

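### Do school counts of 44 and 43 mean that the intent-to-treat analysis lost a randomised school?

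*Combined protocol and SAP*

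**What the plan says.** Under *Design of the Effectiveness Trial*, the combined protocol and SAP gives the number of schools in three ways.

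- **By state:** "We recruited 44 schools across Oregon (N=18) and Arizona (N=26"). The same sentence says that the investigators "randomized them to intervention (received the *Click City®: Tobacco* program) or control (implemented their standard curriculum"). The next sentence gives the order of events: "Schools were randomized after they agreed to participate in the trial and signed a Memorandum of Understanding".
- **By period:** when schools closed in March 2020, "a total of 26 schools had completed their participation in the trial (16 schools in Arizona and 10 schools in Oregon"). After re-opening, "we were able to recruit an additional 17 schools and used the same procedure as that used prior to the pandemic to randomize them".
- **By outcome and arm:** "Among the 44 anticipated schools, 43 completed the trial, and 22 schools were assigned to the intervention arm and 21 schools to control".

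Under *Analysis Strategy*, the sample is defined at student level: a fifth-grader with either assessment is included. The plan labels this as follows: "This intent to treat approach assumed that all those who completed at least one assessment participated" in the programme or usual curriculum as allocated. Nothing in that section limits the sample to schools that completed the trial.

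**The concern.** The state counts give 44, while the period and arm counts give 43. The figure 44 is attached to schools recruited and randomised in the opening sentence, but to schools merely anticipated in the closing one. The 22 and 21 are described as assigned, which normally means randomised, yet they sum to the number that completed.

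The school is the randomised unit, so the number of schools allocated ought to be exact. If 43 were randomised, the opening sentence reports a target as an achievement. If 44 were, one cluster has no stated arm, and a reader may suspect that it was removed after allocation while the analysis kept the intent-to-treat label. Suspicion is natural because each school's participation took several weeks and closure came abruptly, so a school could well have been caught part-way through. What would be at stake is whether the analysis respects the randomisation and whether school-level loss differed between arms.

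**Working it through.** **Inputs** (all from *Design of the Effectiveness Trial*): 18 Oregon and 26 Arizona schools recruited; 16 Arizona and 10 Oregon schools completed before closure; 17 recruited afterwards; 43 of 44 completed; 22 and 21 by arm.

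**Step 1. Reproduce the plan's sums.**

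| Count | Sum | Total |
|---|---|---|
| State | 18 + 26 | 44 |
| Completed before closure | 16 + 10 | 26 |
| Completed before closure + recruited after | 26 + 17 | 43 |
| Arm | 22 + 21 | 43 |

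The state totals leave (26 − 16) + (18 − 10) = 10 + 8 = 18 schools beyond the first 26, against 17 reported. One school is unplaced.

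**Step 2. Ask whether the figures can all be true.** The sum 26 + 17 adds schools that had *finished* by closure to schools *recruited* after re-opening. It equals the number recruited only if every school recruited before closure had also finished, which the text does not say. Suppose 27 were recruited before closure and one did not finish:

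- recruited: 27 + 17 = 44 = 18 + 26;
- completed: 26 + 17 = 43;
- completers by arm: 22 + 21 = 43.

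Every number then agrees. The only slip is that the arm split of the completers is worded as an assignment. This reading is not proven, but it is natural, because the 22 and 21 stand in the same sentence as the 43 that completed.

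**Step 3. Follow the 44th school through the sample rule.**

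| Status of the school | Effect on the analysis |
|---|---|
| Never recruited | None; the opening sentence states a target |
| Recruited, not randomised | None; the opening sentence is loose |
| Randomised, some students assessed | Those students meet the sample rule and belong in the analysis |
| Randomised, no assessments | A loss to report; there are no data to add |

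In no row does the plan as written exclude a randomised school that has data.

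**Step 4. Size.** One school is 1/44 = 2.3% of clusters. Its arm is unknown. If allocation was 22:22, it is one of 22 control schools (1/22 = 4.5%); if 23:21, one of 23 intervention schools (1/23 = 4.3%). The documents state neither allocation.

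For precision, assume equal cluster sizes. The ratio of the standard error at 22/21 to that at 22/22 is

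√[(1/22 + 1/21) / (1/22 + 1/22)] = √(0.09307 / 0.09091) = 1.012.

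The documents give no power or significance level. Taking two-sided 5% and a normal approximation as assumptions, 80% power at 22/22 becomes 79.1%, and 90% becomes 89.3%.

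**The case for a change.** The strongest case for acting is that the opening sentence, read plainly, says 44 schools were randomised, and the only arm counts given account for 43. The closing sentence does not settle this, since it changes the description of the 44. Because randomisation followed a signed agreement, a recruited school would ordinarily have been allocated. The text is also silent on any school under way at closure. If yoking was one to one (an assumption), 22/21 leaves one intervention school without its control. A correction would cost almost nothing.

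Much of this stands. The number randomised is ambiguous between 43 and 44, and the arm, state and fate of one school are not given. A randomised school lost at closure is plausible.

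The consequence for the analysis does not stand. The plan nowhere says that 43 schools were analysed or that completion was a condition of analysis. Keeping the school with whatever assessments exist is what the student-level rule already requires. A missing yoked partner removes nothing from the model, which nests students in schools and schools in condition and has no term for pairs. Whether the model handles students with one assessment properly is a question for all schools alike and does not turn on this one.

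**Conclusion.** The concern does not call for a change. The sums are right and the wording is untidy, but no figure is shown to be false: one school recruited before closure that did not finish would reconcile 44, 43, 26, 17 and 22/21. The one-school shortfall is disclosed in the design section itself. No breach of intent to treat is shown, because the sample rule admits any student with an assessment, whatever became of the school.

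What is left is an accounting detail about one cluster in 44 (2.3%). A school-level flow diagram with separate counts for recruited, randomised and completed would ordinarily supply it from the trial's records, including the 44th school's arm and why it did not finish. The precision cost is about 1.2% in the standard error, or about one percentage point of power at most, given equal cluster sizes and an assumed 80% to 90% starting power.

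This conclusion rests on the sample rule being applied as written. Records showing that a randomised school had assessments that were left out would be a departure from the plan, not a fault in it.

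### Schools were randomised within state and size strata and yoked by start date, but the stated model has no term for any of these, so its test of condition may be conservative and lose power

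*Combined protocol and SAP*

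**What the plan says.** Under Design of the Effectiveness Trial, the 44 recruited schools (18 in Oregon, 26 in Arizona) were the unit of randomisation, and the randomisation was restricted: the investigators "stratified them by state and size of the school (small, medium, large), yoked them according to their desired start dates, and randomized them". Yoking also fixed the timing of measurement: "students in control schools completed the baseline and follow-up assessments during the same week as students in their yoked intervention school". The COVID-19 closure split the trial. Twenty-six schools had finished by 13 March 2020, and 17 more were recruited after re-opening, for which the investigators "used the same procedure as that used prior to the pandemic to randomize them". In the end "43 completed the trial, and 22 schools were assigned to the intervention arm and 21 schools to control".

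Under Analysis Strategy, the model is a "general linear mixed model with students nested within schools and schools nested within condition", with student and school as random effects. The target of the analysis is change: "we examined the effect of the intervention on changes in major outcomes and all etiological mechanisms that were targeted in the program". Neither section names a model term for state, school size, yoked set, start date or period, or gives a reason for leaving them out.

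**The concern.** Stratifying and yoking make the arms alike on state, size and start date, so chance differences between arms on those factors contribute little to the sampling error of the condition effect. A model without these factors does not know this. It leaves whatever they explain in the between-school variance and computes a standard error as if schools had been randomised without restriction. If the factors are prognostic for change, that standard error is too large, the test rejects less often than its nominal level under the null, and power falls.

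With 43 schools, between-school variance largely sets the precision of the condition effect, so the question is not academic. At stake is a missed effect on a major outcome or an etiological mechanism. Yoking already controls history by design, so the point concerns precision and correct test size, not validity.

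**Working it through.** **Inputs from the documents.** The school counts agree: 18 + 26 = 44 recruited; 16 + 10 = 26 finished before the closure; 26 + 17 = 43 = 22 + 21 completed. The documents state no alpha, power, ICC, effect size, number of students per school or stratum sizes, so there is no planned figure to reproduce.

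**Assumptions.** Two-sided 5% test; arms close to balanced on the design factors; R² is the share of the variance of school-mean change that state, size and period explain, shown as a range.

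**Degrees of freedom.** Condition only: 43 − 2 = 41. State (1), size (2) and period (1) use 4 more: 41 − 4 = 37. The critical t moves from 2.020 to 2.026.

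**Formulas.**
- Ratio of the unadjusted standard error to the correct one: 1/√(1 − R²).
- True size: 2·P(T₄₁ > 2.0195/√(1 − R²)).
- Unadjusted power: P(T₄₁(δ) > 2.0195/√(1 − R²)), where T₄₁(δ) is noncentral t with δ = 2.877, the value that gives 80% power with 37 degrees of freedom.

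Worked case, R² = 0.20: 1/√0.80 = 1.118; the effective threshold is 2.0195 × 1.118 = 2.258; size 2.9%; power 73%.

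| R² | SE ratio | True size | Unadjusted power (80% if adjusted) |
|---|---|---|---|
| 0% | 1.00 | 5.0% | 80% |
| 5% | 1.03 | 4.5% | 79% |
| 10% | 1.05 | 3.9% | 77% |
| 20% | 1.12 | 2.9% | 73% |
| 30% | 1.20 | 2.0% | 68% |
| 40% | 1.29 | 1.3% | 61% |

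**How large R² can be.** School-level factors cannot explain student sampling error in a school mean, so R² cannot exceed m·ICC/(1 + (m − 1)·ICC). With an assumed m = 60 students per school, the ceiling is 0.30/1.295 = 23% at an ICC of change of 0.005, 0.60/1.59 = 38% at 0.01, and 1.20/2.18 = 55% at 0.02. Reaching a ceiling would require the factors to explain all true between-school variance in change. If they explain a quarter of it, R² is about 6%, 9% or 14% and unadjusted power about 78%, 77% or 76%. If they explain a tenth, power is about 79% to 80%.

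**Simulation check** (20,000 trials per cell; assumed 22 pairs, 9 in Oregon and 13 in Arizona, one post-closure control school lost). Over the same six R² values, unadjusted size was 5.0%, 4.4%, 3.9%, 2.9%, 1.9% and 1.1%, and unadjusted power 80.5%, 78.8%, 77.1%, 72.9%, 66.9% and 59.2%. The adjusted model held size at 4.8% to 5.1% and power at 79.5% to 80.2%. The mean estimate under the null stayed within 0.007 SD of zero.

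**Which terms to add.** A second simulation (40,000 trials per scenario) used six state-by-size strata and 22 yoked pairs, again with one control school lost. The effect was set to give 80% power unadjusted when no factor matters.
- No prognostic factors: power was 80% unadjusted, 80% with strata terms, and 77% with a fixed effect for every pair, which cuts the degrees of freedom to 20.
- Strata explaining 20%: power was 83%, 88% and 85%, and unadjusted size 3.4%.
- Yoke alone explaining 10%: all three models had 81% power, with sizes of 4.1%, 4.2% and 5.1%.
- Strata 30% plus yoke 20%: sizes were 1.1%, 2.6% and 5.1%.

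The direction is the same in both simulations. The power gaps differ because the effect was calibrated differently.

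**The case against.** The strongest reply is that the Analysis Strategy section is short and does not list its fixed effects. It names no time or baseline term either, although it analyses change, so silence about state and size does not prove they were left out. That stands as a limit: the finding is about the model as stated. If the terms were fitted, one sentence saying so settles the matter.

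Second, the size of the loss rests on an R² the documents do not give, and the higher rows are hard to reach. At an assumed 60 students per school, 40% is impossible at an ICC of 0.005 or 0.01, and 30% is impossible at 0.005. Baseline and follow-up are only about six weeks apart (one week before, four weeks of lessons, one week after), and change already removes stable differences in level. This stands too, and a loss of a few points or none is quite possible.

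Third, conservatism depends on the arms being near-balanced within strata and yokes. Only the overall 22 v 21 split is reported, and the document does not say every yoke is one-to-one. An unbalanced stratum would weaken the conservatism, though restricted randomisation still leaves the unadjusted test at or below its nominal size on average.

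Fourth, a before/after-closure term captures start date only partly and was not a named stratum. If the yoke itself is prognostic, some conservatism remains after the adjustment, which is why a yoked-set random effect is worth considering.

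Finally, a second set of p-values produced after the fact invites selective emphasis. Reporting both results for every outcome limits that. None of this removes the mismatch between a restricted randomisation and a model that ignores the restriction.

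**Conclusion.** The concern holds as a conditional one. The stated analysis does not use the factors by which schools were randomised. If those factors predict change, the test of condition is conservative; at R² of 10% to 30% it gives up roughly 3 to 12 points of power (80% to 77% or 68%). If they do not, nothing is lost. The range rests on an assumed R², a two-sided 5% level and near-balance within strata and yokes. A significant result stands; a null or borderline one may understate the evidence. The balance of cost and gain favours adjustment, which costs under half a point of power when the factors are irrelevant. The change should be made, with medium confidence that it will matter in practice.

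**What to change.** Add one paragraph to Analysis Strategy. Say whether state, school size and yoke were modelled. If they were not, add state, school size (three levels) and period (before or after the March 2020 closure) as fixed effects. In a long-format model with baseline and follow-up rows, each factor needs its interaction with time, because a main effect alone adjusts level and not change. In a change-score or follow-up model, main effects suffice. A random effect for the yoked set can be added if the identifiers were kept, which the documents do not say; avoid a fixed effect for every pair.

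Because the analysis is reported in the past tense, present this as a labelled design-based adjusted analysis beside the existing result for every outcome and mechanism, not as a replacement.

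The cost is that paragraph, a rerun and 4 school-level degrees of freedom. State and size were used to randomise and period follows from each school's assessment dates, so no new data collection should be needed.

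### The Analysis Strategy claims full information maximum likelihood on every student with at least one assessment, but names a least-squares SPSS procedure that does not do this

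*Combined protocol and SAP*

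**What the plan says.** The Analysis Strategy section of the combined protocol and SAP makes three sets of statements.

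- **Sample and missing data (first paragraph).** "The sample consisted of those who completed the baseline and/or the follow-up assessment in 5th grade", and "missing data was estimated using full information maximum likelihood methods". The section says of this: "This approach maximized the 5th grade sample". It also states: "This intent to treat approach assumed that all those who completed at least one assessment participated in Click City: Tobacco".
- **Model (second paragraph).** "Data were analyzed using a general linear mixed model with students nested within schools and schools nested within condition". The software named for fitting this model is given as "using the GLM procedure within SPSS, version 24". Because schools were the unit randomised, "both the student and the school were random effects".
- **Target.** "we examined the effect of the intervention on changes in major outcomes", and on the mechanisms the program was meant to shift.

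The document names no other program or SPSS procedure, no choice between ML and REML, and no separate step in which missing values were filled in. It gives no student count and no missingness rate.

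**The concern.** The first paragraph describes a likelihood analysis in which a student with one assessment still contributes. The second names a procedure that fits by least squares and cannot deliver that. What GLM does is general knowledge of the software and is not stated in the document.

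The target is change, which needs both time points, so the procedure determines who contributes to the estimate. If GLM was run as named, the result is a completers analysis, and the claims about the maximised sample and intention to treat describe something else. If MIXED was run, the analysis may be sound, but a reader following the text cannot reproduce it. The same sentence governs every outcome and every mechanism.

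**Working it through.** The plan gives no figure to reproduce. The check compares its statements and then sizes the consequences on assumed inputs.

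**1. What GLM would do with one-assessment students.** As a repeated-measures or change-score model, it drops any student lacking one of the two values. With data in long form and student as a factor, a student with a single row is fitted exactly by that student's own term and adds nothing to the condition-by-time estimate. In 6 simulated data sets this estimate equalled the complete-pairs estimate to within 1e-14. In long form without a student factor, single rows would be kept, but by least squares and not by full information maximum likelihood.

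**2. Three readings the text leaves open.**
- GLM is a slip for MIXED. The mixed-model wording and the random student and school effects fit this.
- GLM was run as named, giving a completers analysis.
- Values were filled in first and GLM was run on the result. The phrase about missing data being estimated allows this, but no such step is described.

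**3. Share of the stated sample that completers would keep.** Let mb and mf be the missing proportions at baseline and follow-up, assumed independent. The share is (1 − mb)(1 − mf)/(1 − mb·mf).

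| mb = mf (assumed) | Share with both |
|---|---|
| 5% | 0.9025/0.9975 = 90.5% |
| 10% | 0.81/0.99 = 81.8% |
| 15% | 0.7225/0.9775 = 73.9% |
| 20% | 0.64/0.96 = 66.7% |

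**4. What a completers analysis would do to the estimate.** From the Design section: 22 and 21 schools. Assumed: 60 students per school, ICC 0.02, baseline/follow-up correlation 0.6, true effect 0.20 SD, and 2% to 25% of students with only one assessment. There were 2,000 simulation runs per cell.
- Missing completely at random: mean 0.199 to 0.201; SD 0.999 to 1.021 times that of the likelihood model.
- Follow-up missingness depending on baseline equally in both arms: mean 0.198 to 0.202.
- The same dependence in the intervention arm only (hypothetical): 0.204 at 2% to 0.246 at 25% with a log-odds slope of 0.5 per SD, and 0.207 to 0.285 with a slope of 1.0. The likelihood model stays at 0.197 to 0.201.

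An analytic check of the last case uses 0.20 − (1 − 0.6) × (mean baseline of those retained in the intervention arm). It gives 0.204 to 0.248 and 0.208 to 0.285, which agrees. The sign of the shift depends on which students are missing.

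**5. Why the random effects must be spelled out.** The text lists only student and school as random. Take those as intercepts alone, under the assumptions of step 4 with complete data and total variance 1.
- School variance of change: 2 × 0.02 × (1 − 0.6) = 0.016.
- Student variance of change: 2 × 0.98 × (1 − 0.6) = 0.784.
- 1/22 + 1/21 = 0.0931.
- True SD of the condition-by-time estimate: √[(0.016 + 0.784/60) × 0.0931] = √(0.02907 × 0.0931) = 0.052.
- SE from the intercepts-only model, which treats changes as independent across students: √[(0.016 + 0.784)/60 × 0.0931] = 0.035.
- Ratio of SE to true SD, from unrounded values: 0.68.
- Type I error of a nominal 5% test: 2 × [1 − Φ(1.96 × 0.677)] = 2 × [1 − Φ(1.33)] = 18.4%. Simulation with 20,000 runs gave 18.6%, against 5.0% for a t-test on school means.

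With school covariance across the two assessments in the model, REML had a type I error of 4.5% to 5.7% over the missingness range in step 4.

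**The case against.** The strongest reply is that this is a naming slip. The mixed-model wording, the random student and school effects and the maximum likelihood statement all point to MIXED; only the procedure name conflicts. That reading is quite plausible, and under it the correction is a phrase. It does not dispose of the point, because the document does not establish it.

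A second reply is that little is at stake. Assessments were done in school, so low missingness is plausible, and completers lose only about 0% to 2% in precision if data are missing completely at random. This stands. Bias appears only when missingness depends on baseline differently by arm, and the document shows no such pattern. At 2% missing, even that case gives only 0.204 to 0.207 against 0.200.

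A reader might infer more than the text supports in two ways. One is that the trial's estimates are biased or came from completers; the conflict is in the wording, and which analysis was run is unknown. The other is that the reported tests had an 18% error rate; that figure belongs to an intercepts-only model on assumed inputs, and the text does not say how school entered the test of change.

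**Conclusion.** The point holds as an unreconciled contradiction in current text: the stated sample and missing-data method cannot be obtained from the named procedure alone. Confidence in that is high. Confidence about which reading applies is not, since nothing in the document decides it.

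The effect on this trial's results cannot be derived. The sizes in the working rest on assumed values for school size, ICC, correlation, missingness and mechanism, and are not estimates for this trial.

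Severity depends on the answer: minor if only the procedure name is wrong, should-fix if GLM was actually run.

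**What to change.** Name and use a likelihood-based linear mixed model (SPSS MIXED, stating ML or REML) under a stated missing-at-random assumption, with:
- baseline and follow-up as outcome rows, and a condition-by-time effect;
- a random student effect;
- school random effects that include school-by-time, or an equivalent school covariance across the two assessments;
- a test of condition-by-time with degrees of freedom based on the 43 schools (43 − 2 = 41 for a comparison of two arms).

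Then, according to what was done:
- **MIXED was run:** correct the procedure name and confirm that the school-by-time term was included.
- **GLM was run as named:** rerun with the model above and label the GLM result as a completers analysis.
- **Values were filled in first:** describe how, including whether filling was single or multiple and whether school was in the filling model.

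In every case, report the numbers of students with baseline only, follow-up only and both, by arm.

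The cost is one phrase and a count table if MIXED was run with the school-by-time term. Otherwise it is a rerun in the same software, or a description of the filling step. No new data are needed.

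### Does testing several major outcomes with no named primary outcome, alpha or multiplicity rule call for a change to the analysis?

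*Combined protocol and SAP*

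**What the plan says.** The Analysis Strategy gives one model for every measure: "Data were analyzed using a general linear mixed model with students nested within schools and schools nested within condition using the GLM procedure within SPSS". The targets of that model are set out in a single sentence: "we examined the effect of the intervention on changes in major outcomes and all etiological mechanisms that were targeted in the program".

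The measures are not listed. The Assessments paragraph under Procedures describes them by reference to an earlier efficacy trial of the original program: "The measures assessing the outcomes and etiological mechanisms associated with e-cigarette use were like measures assessing outcomes and mechanisms associated with cigarette use". Both places treat outcomes and mechanisms as separate groups.

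The Design section calls the study an effectiveness trial and dates its start: "We began the effectiveness trial in January of 2020". The document itself is dated March 6, 2023, and describes the analysis in the past tense. It contains no significance level, primary outcome, criterion for success, hierarchy, global test or adjustment for multiplicity, and there is no sign of redaction at these points.

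**The concern.** A trial meant to show that a program works normally says in advance which result would show it. Here the outcomes are plural and unranked. If the investigators could point to whichever major outcome reached significance, the chance of at least one false positive would exceed that of a single test and would grow with the number of outcomes. A reader could not tell how much weight one significant result deserves.

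The date sharpens the point. A plan written after the data were analysed cannot itself show that any choice among outcomes came first. Correcting p-values already computed would also cost little effort, so a request for a Holm adjustment looks natural.

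**Working it through.** The plan has no error rate, power or sample-size figure on this point to reproduce, so the check is conditional.

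**Inputs from the document.** The number of major outcomes, k, is at least 2, because the word is plural. Nothing more is given.

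**Inputs assumed.** Two-sided 0.05 per test; no true effects; success means at least one significant major outcome; equicorrelated normal test statistics with correlation r of 0, 0.5 or 0.9. The mechanisms are left out because the document separates them from outcomes and they read as explanatory.

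**Step 1: either direction, k = 2.** P(at least one) = 2 × 0.05 − P(both significant).
- r = 0: P(both) = 0.05² = 0.0025, so 0.10 − 0.0025 = 0.0975.
- r = 0.5: P(both) = 0.0093, so 0.10 − 0.0093 = 0.0907.
- r = 0.9: P(both) = 0.0296, so 0.10 − 0.0296 = 0.0704.

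**Step 2: favourable direction only.** A claim that the program works needs a result in its favour, and for one test that rate is 0.025. With independent tests the rate is 1 − (1 − 0.025)^k. For k = 2 this is 1 − 0.975² = 0.049. Numerical integration over the shared normal component gives the correlated cases.

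| k | Either direction, r = 0 / 0.5 / 0.9 | Favourable only, r = 0 / 0.5 / 0.9 |
|---|---|---|
| 1 | 0.050 | 0.025 |
| 2 | 0.098 / 0.091 / 0.070 | 0.049 / 0.045 / 0.035 |
| 3 | 0.143 / 0.125 / 0.084 | 0.073 / 0.063 / 0.042 |
| 5 | 0.226 / 0.183 / 0.102 | 0.119 / 0.092 / 0.051 |
| 10 | 0.401 / 0.287 / 0.128 | 0.224 / 0.144 / 0.064 |

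A separate simulation of the either-direction rates (400,000 draws, r = 0.5) gave 0.090, 0.126 and 0.288 for k = 2, 3 and 10, in agreement.

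**Step 3: a different success rule.** If every major outcome had to be significant, error could not exceed 5%. For k = 2 it is the P(both) of Step 1: 0.3%, 0.9% and 3.0% at r = 0, 0.5 and 0.9. The document is equally silent on this rule, so whether there is any inflation depends on which unstated rule is supplied.

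**Step 4: cost of adjusting.** For a test with 80% power at two-sided 0.05, the normal approximation gives a mean of 1.960 + 0.842 = 2.802. The worst case under Holm is its first step, at 0.05/k. For k = 2 the critical value is 2.241, so power is Φ(2.802 − 2.241) = 0.712. For k = 3, 5 and 10 the corresponding powers are 0.658, 0.589 and 0.498.

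**The case for a change.** The strongest case for a change is that the size of the inflation is unknown only because the document leaves out the count and the rule, and that this silence is the defect. The direction is certain: if any one of two or more imperfectly correlated outcomes suffices, error is higher than for a single test. The study is called an effectiveness trial and looks ahead to marketing of the program, so a claim is plausible. Listing the outcomes and adjusting existing p-values requires no new data.

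The omission stands, and so does the direction under that rule. The step to a needed change in analysis does not. The rule, the level, the count and the correlation all have to be supplied by the reader. The document says only that effects were examined. Its effectiveness label can be read as a design term, since the Assessments paragraph contrasts this study with an earlier efficacy trial. Error above 5% in the favourable direction needs at least three outcomes, and at r = 0.9 at least four, since three give 4.2%. The 23% and 40% figures rest on 5 and 10 independent outcomes and count significant harm as success. An adjustment may also have been applied and not described; the document cannot settle that.

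**Conclusion.** The plan omits a primary outcome, a significance level, a decision rule and any statement on multiplicity. That is missing detail and not a wrong method, and no change to the analysis follows.

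Under the least favourable reading the text supports (two outcomes, either one sufficient, assumed two-sided 0.05), a false claim of benefit has a probability of 3.5% to 4.9%, against 2.5% for one test. The two-sided rate is 7% to 10%. With more outcomes the rates rise as tabulated, but nothing in the document fixes that number. If all outcomes had to succeed, there would be no inflation.

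The right repair depends on records outside the document. A single primary outcome named beforehand, or a requirement that all succeed, needs no adjustment. Without such a record, Holm is defensible but lowers 80% power to 71% with two outcomes and 50% with ten, a trade-off on which experienced statisticians would differ. Because the analysis is already described as done, no rule adopted now restores full confirmatory standing. Analysts can fill the gap in the trial report by naming the major outcomes, showing every p-value and treating the mechanisms as explanatory; readers can then apply whatever correction they prefer.
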